6.5.3 Potential Cases of Drug-Induced Liver Injury

Abnormal values in AST and/or ALT concurrent or with abnormal elevations in TBL that meet the criteria outlined below, in the absence of other causes of liver injury, are considered potential cases of drug-induced liver injury (eg, Hy's Law) and are always to be considered clinically significant medical events and reported as SAEs.

The 3 "requirements" for Hy's Law are:

1. Evidence that a drug can cause hepatocellular-type injury, generally shown by an increase in serum aminotransferases (AT) elevations $> 3 \times \text{ULN}$ (" $2 \times \text{ULN}$ elevations are too common in treated and untreated subjects to be discriminating").
2. Cases of increased TBL (at least $2 \times \text{ULN}$) with concurrent AT elevations at least $3 \times \text{ULN}$ and no evidence of intra- or extra-hepatic bilirubin obstruction (elevated alkaline phosphatase) or Gilbert's syndrome ([Temple, 2006](#)).
3. No other reason can be found to explain the combination of increased AT and TBL, such as viral hepatitis A, B, or C; preexisting or acute liver disease; or another drug capable of causing the observed injury.

For studies for which a central laboratory is used, alerts will be generated by the central laboratory regarding moderate and severe liver abnormality to inform the Investigator and study team. Subjects should be further evaluated for additional symptoms suggestive of hepatobiliary dysfunction.

6.5.3.1 Definition of Liver Abnormalities

For laboratory abnormalities (including liver) reported as AEs, severity grading assessment should follow the NCI-CTCAE (v4.03) Investigation system organ class.

In addition, the subject should be considered to have **severe hepatic abnormalities for any of the following:**

- ALT or AST > 8 × ULN
- ALT or AST > 5 × ULN for more than 2 weeks
- ALT or AST > 3 × ULN and* TBL > 2 × ULN or international normalized ratio (INR) > 1.5 (If INR testing is applicable/evaluated)
- ALT or AST > 5 × ULN and* TBL > 2 × ULN
- ALT or AST > 3 × ULN with the appearance of fatigue, nausea, vomiting, right upper quadrant pain or tenderness, fever, rash, and/or eosinophilia (> 5%)

* Samples taken simultaneously or within a maximum of 24 hours.

The Investigator may determine that abnormal liver function results, other than those described above, may qualify as moderate or severe abnormalities and require additional monitoring and follow-up.

6.5.3.2 Liver Abnormality Follow-Up Procedures

Confirmed moderate and severe abnormalities in hepatic functions should be thoroughly characterized by obtaining appropriate expert consultations, detailed pertinent history, physical examination, and clinical laboratory tests. Subjects with confirmed abnormal liver function testing should be followed as described below.

Confirmed moderately abnormal liver function tests should be repeated at least once per week, and then weekly or less if abnormalities stabilize and the subject is asymptomatic.

Severe hepatic liver function abnormalities as defined above will be considered an important medical event and should be reported as an SAE. The Sponsor should be contacted and informed of all subjects for whom severe hepatic liver function abnormalities possibly attributable to study drug are observed.

To further assess abnormal hepatic laboratory findings, the Investigator is expected to:

- Obtain a more detailed history of symptoms and prior or concurrent diseases. Symptoms and new-onset diseases are to be recorded as AEs. Illnesses and conditions such as hypotensive events and decompensated cardiac disease that may lead to secondary liver abnormalities should be noted. Nonalcoholic steatohepatitis is seen in obese hyperlipoproteinemic and/or diabetic subjects and may be associated with fluctuating AT levels. The Investigator should ensure that the medical history form captures any illness that predates study enrollment that may be relevant in assessing hepatic function.
- Obtain a history of concomitant drug use (including nonprescription medication, complementary and alternative medications), alcohol use, recreational drug use, and

special diets. Medications, including dose, are to be entered in the eCRF. Information on alcohol, other substance use, and diet should be entered on the eCRF or an appropriate document.

- Obtain a history of exposure to environmental chemical agents.
- Based on the subject's history, other testing may be appropriate including:
 - Acute viral hepatitis (A, B, C, D, E, or other infectious agents such as cytomegalovirus, Epstein-Barr virus)
 - Ultrasound or other imaging to assess biliary tract disease
 - Other relevant clinical laboratory tests including INR, total and direct bilirubin, albumin
- Consider gastroenterology or hepatology consultations.
- Submit results for any additional testing and possible etiology on the eCRF or an appropriate document.

6.5.3.3 Hyperbilirubinemia

Investigations into the nature of liver dysfunction in patients with XLMTM before and after AT132 administration suggest intrahepatic cholestasis as a likely central feature. Ursodiol is an enterally administered hydrophilic bile acid that can decrease the hydrophobic bile acid content within bile ([Poupon, 2012](#)). As hydrophilic bile acids are generally non-toxic to hepatocytes, hydrophobic bile acids can be toxic to these same cells in direct contact, ursodiol has been used to treat severe cholestatic syndromes, such as progressive intrafamilial intrahepatic cholestasis ([Balistreri, 1997](#); [Strauss, 2006](#); [Suskind, 2006](#)) and intra-hepatic and extra-hepatic cholestatic diseases in childhood ([Kriegermeier, 2020](#)). Ursodiol has also been used for prophylaxis of hepatic veno-occlusive disease ([Cheuk, 2015](#)). Subjects in this study will begin treatment with prophylactic ursodiol prior to AT132 administration, as described in [Section 4.5](#).

7 STATISTICAL CONSIDERATIONS

The Statistical Analysis Plan (SAP) will provide a detailed description of the planned statistical analyses and data summaries. This section presents an overview of the planned analyses. Final analyses are not limited to the summaries described herein. If discrepancies exist between the text of the statistical analysis as planned in the protocol and the final SAP, the final SAP will define the planned analysis of record. Reasons for such discrepancies, will be described in the final study report.

Data listings and summaries will be presented for all subjects and by dose levels. All continuous study assessments will be summarized using descriptive statistics (ie, n, mean, standard deviation, median, Q1, Q3, minimum, and maximum). All categorical study assessments will be summarized by time point, as applicable, using frequency counts and percentages. Details for the efficacy analyses will be provided below and in the SAP.

As of protocol v9 and beyond: The 1.0×10^{14} vg/kg dose level based on a 1st generation titer method equates to 1.3×10^{14} vg/kg as determined by a 2nd generation vg titer assay (see [Section 1.4.2](#)); and the 3.0×10^{14} vg/kg dose level equates to 3.5×10^{14} vg/kg based on an analysis of the historical Study ATX-MTM-002 drug product lots using the 2nd generation vg titer assay.

The study is no longer able to address the stated objectives, hence the statistical analysis will provide descriptive summaries by treatment groups.

7.1 Sample Size

The following language was from protocol v9 that planned a formal analysis to compare 1.3×10^{14} vg/kg and delayed-treatment control, however given that the study will not be able to address the objectives, no such formal analysis will be conducted.

A power analysis for the primary analysis of the primary endpoint was conducted at 80% power and 0.05 level of alpha to estimate the required sample size based on Mean of 13.0 vs. 0.0 hours of reduction in ventilation need, with common SD of 6.0 by Week 24 using a t-test, resulting in at least $N = 10$ for a balanced 1:1 allocation between 1.0×10^{14} vg/kg AT132 (equates to 1.3×10^{14} vg/kg as determined by the 2nd generation vg titer assay) and delayed-treatment control. It is further assumed, that the same difference in means (SD), will provide at least 80% power using a Mixed Effect Model Repeat Measurement (MMRM) analysis proposed for the primary endpoint. However, it is possible that 1:1 allocation may not be feasible; 1 control subject serving as control for multiple treated subjects, or multiple control subjects being a match for a single treated subject. Therefore, all qualified control subjects will be used in the analyses to ensure adequate power is available to detect the intended difference between treated and control subjects.

7.2 Analysis Populations

The following analysis sets for subjects treated with AT132 will be used:

- Full Analysis Set (FAS) is defined as all randomized and/or enrolled subjects who received AT132 and had at least 1 postdose efficacy assessment. The FAS will be used for the primary analysis of the primary efficacy endpoint.
- Safety Analysis Set (SAF) is defined as all randomized and/or enrolled subjects who received AT132. The SAF will be used for the analysis of the safety endpoints.

In each analysis set, 3 treatment groups are defined by: (i) subjects treated at 1.3×10^{14} vg/kg (low dose), (ii) subjects treated at 3.5×10^{14} vg/kg (high dose), and (iii) all subjects treated with AT132 (overall; not applicable to efficacy endpoints).

7.3 Subject Disposition, Demographic Data, Baseline Characteristics, and Extent of Exposure

The number and percentage of study subjects who complete and discontinue the study as well as reasons for early discontinuation will be presented by low dose, high dose, and overall for the SAF.

Demographic and baseline measurements will be summarized by low dose, high dose, and overall on the FAS and SAF. Medical history will be summarized by low dose, high dose, and overall for the SAF.

Exposure will be confirmed based on the report of dosing recorded in the eCRF, and will be presented in a listing.

7.4 Statistical Analysis

7.4.1 Safety Analyses

The analysis of safety endpoints will be conducted by treatment group (low dose, high dose, and overall) for the SAF.

7.4.1.1 Adverse Events

AEs will be coded using the Medical Dictionary for Regulatory Activities (MedDRA) dictionary.

Events will be identified as treatment-emergent (TEAE) and non-treatment-emergent (non-TEAE) on the basis of the date of onset relative to the date of AT132 dosing.

Number and percentage of subjects with TEAEs classified by system organ class (SOC) and preferred term (PT); by severity, causality, seriousness, and action taken with regard to study drug will be summarized. Number (%) of subjects with TEAEs leading to discontinuation of study will also be summarized. Hospitalization will be summarized by frequency (%) and duration. TEAEs and/or hospitalizations may be annualized.

7.4.1.2 Laboratory and Other Safety Evaluations

For clinical safety laboratory test results, vital signs, and ECG parameters, the numeric values and corresponding changes from baseline will be summarized using descriptive statistics by parameter and time point.

Incidence of laboratory abnormalities that increase at least 1 toxicity grade from baseline at any time postbaseline will be summarized. If baseline data are missing, then any graded abnormality (ie, at least a Grade 1) will be considered.

ECHO findings, liver ultrasounds, antibody formation (anti-AAV8, anti-MTM1), and viral shedding will be summarized.

Change in special liver laboratory parameters of interest (eg, bilirubin, AST, ALT, and CK) will be summarized.

7.4.2 Efficacy Analysis

7.4.2.1 Analysis of Primary Efficacy Endpoint

The primary efficacy endpoint is change from baseline in hours of ventilation support at Week 24. The hours of ventilation support will be based on diary data from subjects for whom diary data was collected at baseline (those administered AT132 under protocol v5 and beyond, including all subjects in Part 2), and by assessment of time off ventilator questionnaire for all other subjects (those administered AT132 under protocol v4 and prior). Weekly scores will be the average of ventilation hours needed for at least 5 out of the 7 days. Missing values will be ignored if number of ventilation hours are available for at least 5 days, otherwise they will be imputed by the worst score of the week.

7.4.2.1.1 Primary Analysis

The primary efficacy endpoint will be analyzed using a MMRM with baseline, treatment (low dose or high dose), time (Weeks 1, 4, 12, 16, 24, 36, and 48), and treatment by time interaction as fixed effects and subject as random effect. The change from baseline in hours of ventilation support at Week 24 will be summarized by treatment group based on this model. The primary analysis will be conducted using the FAS.

7.4.2.1.2 Secondary Analysis

Based on the MMRM described in [Section 7.4.2.1.1](#), the change from baseline in hours of ventilation support at Week 1, 4, 12, 16, 36, and 48 will be summarized by treatment group.

7.4.2.2 Analysis of Secondary Efficacy Endpoints

7.4.2.2.1 Key Secondary Efficacy Endpoints

The analysis of key secondary efficacy endpoints will be conducted using the FAS.

The number and percentage of subjects achieving functionally independent sitting for at least 30 seconds by Week 24 will be summarized by low dose and high dose.

7.4.2.2 Other Secondary Efficacy Endpoints

The analysis of other secondary efficacy endpoints will be conducted using the FAS.

Time to reduction in required daily ventilator support to \leq 16 hours by Week 24, time to reduction of at least 6 hours in daily ventilator support by Week 24, and time to death will be summarized for low dose and high dose. Kaplan-Meier plots along with median (95% CI) time from the study start date to event will be provided.

The CHOP INTEND, MIP, ACEND, and PedsQL, as well as their changes from baseline, will be summarized descriptively over time, and the changes from baseline will be analyzed using the MMRM in a similar method to that used for the primary analysis of the primary efficacy endpoint.

The number and percentage of subjects attaining age-appropriate clinically relevant gross motor function milestones through Week 24, and subjects achieving full ventilator independence at Week 24, will be summarized for low dose and high dose.

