Following the occurrence of fatal serious AEs (SAEs) in Study ATX-MTM-002, the Sponsor, in consultation with the DMC and external experts, evaluated the data and reassessed the benefit/risk profiles of the 1.0×10^{14} vg/kg and 3.0×10^{14} vg/kg dose levels. As of the data cutoff date of 08 July 2020, 5 subjects who received 3.0×10^{14} vg/kg AT132 developed AT132-related SAEs involving the hepatobiliary system. In 2 subjects, these SAEs resolved; in 3 subjects, fatal events occurred subsequent to severe cholestatic liver dysfunction. Within the 3.0×10^{14} vg/kg dose level cohort, 8 of 17 subjects (47.1%) experienced 26 SAEs considered related to AT132. In contrast, within the 6 subjects dosed at the 1.0×10^{14} vg/kg dose level, all of whom are ≥ 2 years from AT132 administration, 1 (16.7%) subject experienced 4 AT132-related SAEs, all resolved, and none involved the hepatobiliary system. In addition to a favorable safety profile observed in the subjects treated with 1.0×10^{14} vg/kg, a clinically meaningful benefit continues to be observed in this group at last follow-up. In this group, which had a mean 20.5 hours (SE 2.02) of ventilation per day at baseline ($n = 5$ [83.3%] with invasive ventilation; $n = 1$ [16.7%] with non-invasive ventilation), 5 out of 6 (83.3%) subjects were ventilatory independent at last follow-up (as of data cutoff date 08 July 2020). With respect to gross motor development, at baseline 5 of the 6 subjects did not perform any of the following major motor milestones: sit unassisted for 30 seconds, raise self to standing position, stand alone, or walk alone. At baseline, 1 subject did sit unassisted for 30 seconds but did not perform the remaining motor tasks. At last follow-up following AT132 administration at 1.0×10^{14} vg/kg, 5 out of 6 subjects performed all of these motor tasks, including walking alone. Regarding performance on the Children's Hospital of Philadelphia Infant Test of Neuromuscular Disorders (CHOP INTEND), this 1.0×10^{14} vg/kg group demonstrated a baseline mean score of 37.7 (SE 2.42). At last follow-up, performance had improved to a mean score of 56.5 (3.97).

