3.3 Selection of Study Population

3.3.1 Inclusion Criteria

Subjects must meet all of the following inclusion criteria to be eligible for participation in this study. Subjects assigned to delayed-treatment control will be evaluated to confirm the subject still meets a subset (*) of the inclusion/exclusion criteria before receiving AT132.

1. Subject has a diagnosis of XLMTM resulting from a genetically confirmed mutation in the *MTM1* gene as assessed by a Sponsor-approved testing facility.*
2. Subject is male.*
3. Subject is aged less than 5 years old at dosing.*
4. Subject requires mechanical ventilatory support:
 - Part 1: Subject requires some mechanical ventilatory support (eg, ranging from 24 hours per day fulltime mechanical ventilation, to noninvasive support such as continuous positive airway pressure [CPAP] or bilevel positive airway pressure [BiPAP] during sleeping hours).
 - Part 2: Subject requires invasive mechanical ventilatory support ranging from 20 to 24 hours per day at screening (confirmed by daytime polysomnographic study).
5. Subject requiring invasive mechanical ventilator support is fitted with or willing to be fitted with a cuffed tracheostomy tube for some respiratory assessments.*
6. Subject has ventilator maximum positive end-expiratory pressure (PEEP) < 8 cmH₂O at screening.*
7. Signed informed consent by the parent(s) or legally authorized representative (LAR) (when applicable).*
8. Subject and parent(s)/LAR(s) are willing and able to comply with study visits and study procedures.*
9. UNIQUE to France: Subject's weight is ≥ 4.8 kg.

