4.4.2.2 Main Analytical Approach

The secondary efficacy analyses will be conducted for the FAS.

4.4.2.2.1 Time to reduction in required ventilator support to ≤ 16 hours a day (only in participants who require invasive ventilation) at Week 24

This endpoint will be summarized for low dose and the high dose groups separately in the participants who require invasive ventilation. Kaplan-Meier plots along with median (95% CI) time from the study start date to event will be provided.

The number of hours of ventilator support at each collected time point for this analysis will be taken directly from the daily diary (Protocol V5.0 and later) or by assessment of time off ventilator questionnaire (prior to Protocol V5.0). The first instance of time reduction reported as ≤ 16 hours per day will be considered an event. Participants will be censored at either Week 24 or withdrawal from study, whichever occurs first.

4.4.2.2.2 Change from baseline in Children's Hospital of Philadelphia Infant Test of Neuromuscular Disorders (CHOP INTEND) at Week 24

The change from baseline will be analyzed using the MMRM in a similar method to that used for the primary analysis of the primary efficacy endpoint, described in [Section 4.3.2](#).

Estimated change from baseline in CHOP INTEND score at Week 24 will be summarized by dose level.

In addition, the CHOP INTEND score and corresponding change from baseline at each visit will be summarized descriptively by dose level group.

The CHOP INTEND is an assessment scale that was originally designed to quantify motor abilities in infants aged 1.4 to 37.9 months, with spinal muscular atrophy type I (SMA-I) ([Glanzman, 2010](#)) and has been validated for XLMTM ([Duong, 2021](#)). The scale contains 16 questions, each of which is scored on a scale of 0 to 4, with 0 being no response/ability to perform the movement and 4 highest ability to perform the task, per CHOP INTEND item instructions.

The score used for analysis is the total sum of all 16 questions, which will range from 0 to 64. Higher score indicates better neuromuscular function. If an item is missing or scored as "Could Not Test (CNT)" then 0 will be imputed for the item score.

If a participant has 2 assessments with a total score of ≥ 56 , the CHOP INTEND will not be required for future visits.

Subject line plots of the CHOP INTEND over time will be created.

4.4.2.2.3 Change from baseline in maximal inspiratory pressure (MIP) at Week 24

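### The protocol's analysis of time to a 6 h/day reduction in ventilator support is missing from the governing SAP, leaving only a ≤16 h/day target whose difficulty depends on baseline

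*Protocol*

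**What the plan says.** Protocol 7.4.2.2.2 (Other Secondary Efficacy Endpoints) names three time-to-event summaries for the FAS, by low and high dose with Kaplan-Meier plots: time to ≤16 h/day of ventilator support, "time to reduction of at least 6 hours in daily ventilator support by Week 24", and time to death.

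Protocol Section 7 states that where the two documents differ, "the final SAP will define the planned analysis of record", with the reasons to be given in the study report.

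The SAP carries two of the three. Survival is in 4.4.2.2.8. The ≤16 h/day analysis is in 4.4.2.2.1, where the event rule is "The first instance of time reduction reported as ≤ 16 hours per day will be considered an event" and the population is restricted: "This endpoint will be summarized for low dose and the high dose groups separately in the participants who require invasive ventilation". Children without an event are censored at Week 24 or at withdrawal. The 6-hour analysis is in neither SAP endpoint list (1.1.2 and 4.4.2.1) nor in any methods section, and the SAP version history does not mention it.

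The protocol's endpoint lists, in the synopsis and in Section 2, also give only the ≤16 h/day endpoint. The 6-hour analysis therefore stands in Protocol 7.4.2.2.2 alone.

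**The concern.** As the documents stand, an analysis that the protocol says will be done will not be done, and nothing explains why. The text does not look like an overlooked remnant. The version 12 amendment edited this same protocol section, removing a qualifier from the ventilator-independence endpoint, and left the 6-hour wording in place. The SAP history marks two other departures as changes from the protocol but says nothing about this one.

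The two ventilator analyses also answer different questions. A fixed ceiling of 16 h/day asks more of a child who starts at 24 h/day than of one who starts at 20 h/day. A 6-hour reduction asks the same of both. With only the ceiling left, a child can reach the event earlier because of a lower starting point and not because of a larger response. If baseline hours differed between the dose groups, the displayed dose curves would partly reflect that difference.

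**Working it through.** **The plan's own figure.** The planning inputs are in Protocol 7.1: "Mean of 13.0 vs. 0.0 hours of reduction in ventilation need, with common SD of 6.0 by Week 24 using a t-test". For a two-sample t-test (noncentral t, two-sided 0.05; the sidedness is my assumption), 4 per arm gives 72.4% power and 5 per arm gives 85.0%. The minimum is 5 per arm, N = 10, as stated. That calculation is historical, but it confirms how the 13 h and 6 h are to be read.

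**Reduction required for ≤16 h/day.** Required reduction = baseline − 16:
- from 24 h/day: 24 − 16 = 8 h
- from 20 h/day: 20 − 16 = 4 h
- at or below 16 h/day: 0 h. The SAP has no rule for an invasively ventilated child who starts there, so the first record could count as the event.

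The Part 2 entry rule (Protocol 3.3.1) is "Part 2: Subject requires invasive mechanical ventilatory support ranging from 20 to 24 hours per day at screening", so the required reduction varies two-fold within that range alone.

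**Probability of meeting each target at Week 24.** P = Φ((mean reduction − required reduction) / 6). The 13 h mean is the protocol's; 10 h and 8 h are assumed smaller effects.

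| Mean reduction | ≤16 h from 24 h | ≤16 h from 20 h | ≥6 h reduction, either baseline |
|---|---|---|---|
| 13 h | Φ(5/6) = 79.8% | Φ(9/6) = 93.3% | Φ(7/6) = 87.8% |
| 10 h | Φ(2/6) = 63.1% | Φ(6/6) = 84.1% | Φ(4/6) = 74.8% |
| 8 h | Φ(0) = 50.0% | Φ(4/6) = 74.8% | Φ(2/6) = 63.1% |

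**Timing.** Suppose the 13 h accrues linearly over 24 weeks (an assumption). Then ≤16 h is reached at 24 × 8/13 = week 14.8 from 24 h/day and at 24 × 4/13 = week 7.4 from 20 h/day. A 6 h reduction is reached at 24 × 6/13 = week 11.1 from either.

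**Do the analysed dose groups differ at baseline?** The documents cannot settle this.
- Entry rules differed. Part 1 was wider, down to non-invasive support during sleep: "Part 1: Subject requires some mechanical ventilatory support".
- For the first six low-dose children, Protocol 1.4.2 reports a group "which had a mean 20.5 hours (SE 2.02) of ventilation per day at baseline", so SD = 2.02 × √6 = 4.9 h. One of the six was on non-invasive support and is outside the ≤16 h analysis.
- That one child could account for all of the spread. With five children at a and one at a − d, the SE is d/6 and the mean is a − d/6. Setting d/6 = 2.02 gives d = 12.1 and a = 22.5, so five children at about 22.5 h and one at about 10.4 h fit the reported mean and SE. This is one possible pattern, not a finding.
- No high-dose baseline is reported.

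**The case against.** The best defence is that this is a loose phrase and not a lost endpoint. All four endpoint lists, two in each document, name only ≤16 h/day, so the SAP agrees with the protocol's declared endpoints and 7.4.2.2.2 is the outlier. Deleting the phrase would reconcile the documents as well as adding the analysis would. That stands, and the fix allows for it. A reader might also infer that the sponsor removed the analysis from the SAP without recording it. The documents do not support that: the history lists changes from prior SAP versions, which are not available here, and the analysis may never have been in one.

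A second tempting inference is that the dose groups do differ at baseline, so that the ≤16 h curves are biased. This is not shown. High dose is not the same as Part 2, because Cohort 2 received the high dose under the wider Part 1 rule. The 20.5 h low-dose mean includes a child whom the ≤16 h analysis excludes. The restriction to invasive ventilation may itself remove much of the spread.

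Third, a baseline-relative view survives. SAP 4.3.2 models change in ventilation hours with baseline as covariate in the whole FAS, and adds by-visit summaries and individual line plots. With so few children, those plots let a reader see most 6-hour reductions. This stands, but none of it is a time-to-response summary.

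Fourth, the 6-hour criterion is not free of baseline everywhere: it cannot be met from below 6 h/day. That is correct, but it does not arise in the 20 to 24 h range.

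**Conclusion.** The point holds as an unexplained inconsistency between protocol and SAP, with a conditional consequence for interpretation. What is lost is a time-to-response result that does not become easier as baseline falls within the 20 to 24 h/day range.

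On the planning figures, the same benefit gives 79.8% or 93.3% reaching ≤16 h/day depending on baseline, a gap of 13.5 percentage points, where the 6-hour criterion gives 87.8% at both. These figures are illustrative. They assume normal reductions of equal size at every baseline, ignore the floor at 0 h, and describe status at Week 24 and not the first qualifying reading. Whether the dose curves are affected depends on the baseline hours of the invasively ventilated children in each group, which the documents do not give.

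Both documents now limit the statistics to descriptive summaries, and the SAP rules out hypothesis testing. No primary or key secondary result, test or error rate is touched. The change is worth making because it is cheap and the protocol already calls for the analysis.

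**What to change.** Add the analysis to SAP 4.4.2.2 as a descriptive Kaplan-Meier summary by dose:
- **Population:** FAS children with a baseline of at least 6 h/day, whatever the type of ventilation.
- **Event:** first reading at least 6 h/day below the child's own SAP 4.3.1 baseline. State explicitly that a single reading is compared with a baseline that, for diary participants, is a weekly average.
- **Data source and censoring:** as for the ≤16 h/day analysis.
- **Time origin:** AT132 dosing for both ventilator curves. The ≤16 h/day analysis is currently timed from the study start date, whereas SAP survival is timed from dosing. Without a common origin the two ventilator curves cannot be compared.

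Report it next to the ≤16 h/day result, align the endpoint lists in both documents, and record the change in the SAP history. If the sponsor prefers not to run it, delete it from Protocol 7.4.2.2.2 and state the reason.

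The cost is one SAP paragraph, a changed time origin for the existing curve, and one further table and figure from data already collected. The downside is one more descriptive result to read.
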